9.3.5.1. Laboratory Measures and Vital Signs

Laboratory measures and vital signs will be summarized for each scheduled visit by

- actual measures at baseline and postbaseline
- change from baseline to postbaseline, or
- percent change from baseline to postbaseline.

The laboratory measures may be log transformed before statistical analyses, if deemed necessary. Continuous variables, as well as the change from baseline for these variables or other appropriate transformed variables, will be analyzed by MMRM models as described in Section 9.3.1.

The percentages of participants with treatment-emergent abnormal, high, or low measures, including laboratory and vital signs, will be summarized and compared between treatment groups using Fisher's exact test.

The analysis details will be provided in the SAP.

9.3.6. Pharmacokinetic and Pharmacodynamic Analyses

A population PK approach using nonlinear mixed-effects modeling will be used to summarize and analyze LY3561774 concentration data.

The relationships between LY3561774 dose and concentration and selected efficacy and safety endpoints may be characterized. Additionally, the impact of intrinsic and extrinsic factors, such as age, weight, gender, and liver function on PK and PD parameters, may be examined as needed.

If anti-drug antibody titers are detected from immunogenicity testing, then the impact of immunogenicity titers on LY3561774 PK or any relevant efficacy parameters may also be examined. Additional analyses may be conducted if they are deemed appropriate.

9.3.7. Immunogenicity Assessments

If data from validated immunogenicity assays are available, TE-ADAs may be assessed.

Treatment-emergent ADAs are defined as participants

- with a 2-fold (1 dilution) increase in titer than the minimum required dilution if no ADAs were detected at baseline (treatment-induced ADA), or

- with a 4-fold (2 dilutions) increase in titer compared with baseline if ADAs were detected at baseline (treatment-boosted ADA).

The frequency and percentage of participants with preexisting ADA and who are TE-ADA positive (TE-ADA+) to LY3561774 will be tabulated.

The distribution of titers and frequency of neutralizing antibodies (if assessed) for the TE-ADA+ participants may also be tabulated.

The relationship between the presence of antibodies and PK parameters, efficacy response or safety to LY3561774 may also be assessed. Additional details may be provided in the SAP.

9.3.8. Subgroup Analyses

Subgroup analyses of important factors, such as age, sex, ethnicity, baseline TG, and other factors to be specified in the SAP, are planned for the key outcomes.

The models used for these analyses will vary depending on the subgroups and the outcome. Other exploratory subgroup analyses may be performed as deemed appropriate.

Details of the modeling will be provided in the SAP.

9.4. Interim Analysis

A first planned interim analysis may be conducted when at least 50% of participants complete Day 120 (Visit 7) or discontinue treatment. There may be 2 more interim analyses after the first interim analysis and before final analysis (100% of patients complete 180 days of study or discontinue treatment). These 3 interim analyses will be for the purpose of internal planning and decision making and may assess safety, PK, or efficacy measures. The SAP will describe the interim analysis in greater detail.

If an unplanned interim analysis is deemed necessary for reasons other than a safety concern, the protocol must be amended.

An interim assessment committee (IAC) will be formed to review the interim analyses for totality of data including the safety and efficacy reports in an unblinded manner (Section 10.1.5). Details on the timing of the interim analyses, operational support, and unblinding will be specified in the IAC charter and in the study unblinding plan.

Information that may unblind the study during the analyses will not be reported to study sites or blinded study team members before the study has been unblinded until final database lock. Study sites will receive information about interim results only if deemed necessary for the safety of the participants. The study will not be stopped based on the superiority of LY3561774 versus placebo. Therefore, there will be no inflation of the type 1 error rate, and no need to employ an alpha spending function or multiplicity adjustment.

The primary database lock and primary data analysis for study EZCB will occur when all participants have completed 180 days (Visit 9) of treatment. Another efficacy and safety assessment will occur when all participants have completed 270 days (Visit 12) of the treatment. The final database lock and final data analysis will occur when all randomized participants have completed the study. Participants and investigators will remain blinded until the completion of the study.

9.5. Sample Size Determination

The sample size calculation is based on the primary efficacy estimand and its endpoint, percent change from baseline at Day 180 in ApoB.

Approximately 175 participants will be randomly assigned in a 2:1:2:2 ratio to placebo: LY3561774 100 mg:400 mg:800 mg. Assuming a 20% dropout rate, this results in approximately 20 completers for 100 mg group and 40 completers per arm for the rest of the groups.

Assuming a standard deviation of 15%, and a 2-sided alpha level of 0.05, the completers for each treatment arms will provide >99% power to detect a treatment difference of -30% for the primary endpoint.

10. Supporting Documentation and Operational Considerations

10.1. Appendix 1: Regulatory, Ethical, and Study Oversight Considerations

10.1.1. Regulatory and Ethical Considerations

This study will be conducted in accordance with the protocol and with the following:

- Consensus ethical principles derived from international guidelines including the Declaration of Helsinki and CIOMS International Ethical Guidelines
- Applicable ICH GCP Guidelines
- Applicable laws and regulations

The protocol, protocol amendments, ICF, IB, and other relevant documents (for example, advertisements) must be submitted to an IRB/IEC by the investigator and reviewed and approved by the IRB/IEC before the study is initiated.

Any amendments to the protocol will require IRB/IEC approval before implementation of changes made to the study design, except for changes necessary to eliminate an immediate hazard to study participants.

Protocols and any substantial amendments to the protocol will require health authority approval prior to initiation except for changes necessary to eliminate an immediate hazard to study participants.

The investigator will be responsible for the following:

- Providing written summaries of the status of the study to the IRB/IEC annually or more frequently in accordance with the requirements, policies, and procedures established by the IRB/IEC.
- Notifying the IRB/IEC of SAEs or other significant safety findings as required by IRB/IEC procedures.
- Providing oversight of study conduct for participants under their responsibility and adherence to requirements of 21 Code of Federal Regulations (CFR), ICH guidelines, the IRB/IEC, European regulation 536/2014 for clinical studies (if applicable), and all other applicable local regulations.

Investigator sites are compensated for participation in the study as detailed in the CTA.

10.1.2. Financial Disclosure

Investigators and sub-investigators will provide the sponsor with sufficient, accurate financial information as requested to allow the sponsor to submit complete and accurate financial certification or disclosure statements to the appropriate regulatory authorities. Investigators are responsible for providing information on financial interests during the course of the study and for 1 year after completion of the study.

10.1.3. Informed Consent Process

The investigator or the investigator's representative will explain the nature of the study, including the risks and benefits, to the participant and answer all questions regarding the study.

Participants must be informed that their participation is voluntary. Participants will be required to sign a statement of informed consent that meets the requirements of 21 CFR 50, local regulations, ICH guidelines, privacy and data protection requirements, where applicable, and the IRB/IEC or study center.

The medical record must include a statement that written informed consent was obtained before the participant was entered in the study and the date the written consent was obtained. The authorized person obtaining the informed consent must also sign the ICF.

Participants must be re-consented to the most current version of the ICF(s) during their participation in the study.

A copy of the ICF(s) must be provided to the participant and is kept on file.

Participants who are rescreened are required to sign a new ICF.

10.1.4. Data Protection

Participants will be assigned a unique identifier by the sponsor. Any participant records, datasets or tissue samples that are transferred to the sponsor will contain the identifier only; participant names or any information which would make the participant identifiable will not be transferred.

The participant must be informed that the participant's personal study-related data will be used by the sponsor in accordance with local data protection law. The level of disclosure must also be explained to the participant who will be required to give consent for their data to be used as described in the informed consent.

The participant must be informed that their medical records may be examined by clinical quality assurance auditors or other authorized personnel appointed by the sponsor, by appropriate IRB/IEC members, and by inspectors from regulatory authorities.

The sponsor has processes in place to ensure data protection, information security and data integrity. These processes include appropriate contingency plan(s) for appropriate and timely response in the event of a data security breach.

10.1.5. Committees Structure

Internal assessment committee (IAC)

If there are unplanned interim analyses, an IAC will review the interim efficacy and safety data in an unblinded fashion.

The IAC will be fully independent from the study team and will include, at a minimum, a Lilly medical physician and a statistician. Details about IAC membership, purpose, responsibilities, and operation will be described in an IAC charter, which will be approved prior to the first unblinding.

Participant safety will be continuously monitored by the sponsor's blinded internal safety review team, which includes safety signal detection at any time during the study.

All safety data collected will be summarized and reviewed by the sponsor's internal safety review committee for agreement of next steps.

Evaluation of unblinded safety data by the IAC will occur if any of these events are observed following review by the blinded safety review team

- three or more participants experience hematologic TEAE graded as severe by the investigator and are judged as related to blinded study treatment by the investigator
- three or more participants experience MACE, or
- a malignancy SAE occurs during the study.

Enrollment and dosing may be paused during the review by the IAC.

Case unblinding may be performed for above reviews if necessary.

External clinical endpoint committee

An independent clinical endpoint committee, external to Lilly, will be formed to adjudicate MACE and deaths. This committee will be blinded to treatment assignment.

10.1.6. Dissemination of Clinical Study Data

Reports

The sponsor will disclose a summary of study information, including tabular study results, on publicly available websites where required by local law or regulation.

Data

The sponsor provides access to all individual participant data collected during the trial, after anonymization, with the exception of PK or genetic data. Data are available for request 6 months after the indication studied has been approved in the US and EU and after primary publication acceptance, whichever is later. No expiration date of data requests is currently set once data are made available.

Access is provided after a proposal has been approved by an independent review committee identified for this purpose and after receipt of a signed data sharing agreement. Data and documents, including the study protocol, SAP, CSR, blank or annotated CRFs, will be provided in a secure data sharing environment for up to 2 years per proposal.

For details on submitting a request, see the instructions provided at www.vivli.org.

10.1.7. Data Quality Assurance

Investigator responsibilities

All participant data relating to the study will be recorded on printed or electronic CRFs unless transmitted to the sponsor or designee electronically (for example, laboratory data).

The investigator is responsible for verifying that data entries are accurate and correct by physically or electronically signing the CRF.

The investigator must maintain accurate documentation (source data) that supports the information entered in the CRF.

The investigator must permit study-related monitoring, audits, IRB/IEC review, and regulatory agency inspections and provide direct access to source data documents.

Data monitoring and management

Quality tolerance limits will be predefined to identify systematic issues that can impact participant safety and/or reliability of study results. These predefined parameters will be monitored during the study and important excursions from the QTLs and remedial actions taken will be summarized in the CSR.

Monitoring details describing strategy, for example, risk-based initiatives in operations and quality such as risk management and mitigation strategies and analytical risk-based monitoring, methods, responsibilities and requirements, including handling of noncompliance issues and monitoring techniques are provided in the Monitoring Plan.

The sponsor or designee is responsible for the data management of this study including quality checking of the data.

The sponsor assumes accountability for actions delegated to other individuals (for example, contract research organizations).

Study monitors will perform ongoing source data verification to confirm that data entered into the CRF by authorized study personnel are accurate, complete, and verifiable from source documents, that the safety and rights of participants are being protected, and that the study is being conducted in accordance with the currently approved protocol and any other study agreements, ICH GCP, and all applicable regulatory requirements.

Records retention and audits

Records and documents, including signed ICFs, pertaining to the conduct of this study must be retained by the investigator for the time period outlined in the CTA unless local regulations or institutional policies require a longer retention period. No records may be destroyed during the retention period without the written approval of the sponsor. No records may be transferred to another location or party without written notification to the sponsor.

In addition, sponsor or its representatives will periodically check a sample of the participant data recorded against source documents at the study site. The study may be audited by sponsor or its representatives, and/or regulatory agencies at any time. Investigators will be given notice before an audit occurs.

Data capture system

The investigator is responsible for ensuring the accuracy, completeness, legibility, and timeliness of the data reported to the sponsor.

Electronic data capture system

An EDC system will be used in this study for the collection of CRF data. The investigator maintains a separate source for the data entered by the investigator or designee into the sponsor-provided EDC system. The investigator is responsible for the identification of any data to be considered source and for the confirmation that data reported are accurate and complete by signing the CRF.

Data storage and access

Data collected via the sponsor-provided data capture systems will be stored at third parties.

The investigator will have continuous access to the data during the study and until decommissioning of the data capture systems. Prior to decommissioning, the investigator will receive or access an archival copy of pertinent data for retention.

Data managed by a central vendor, such as laboratory test data, will be stored electronically in the central vendor's database system and reports will be provided to the investigator for review and retention. Data will subsequently be transferred from the central vendor to the sponsor data warehouse.

Data from complaint forms submitted to the sponsor will be encoded and stored in the global PC management system.

10.1.8. Source Documents

Source documents provide evidence for the existence of the participant and substantiate the integrity of the data collected. Source documents are filed at the investigator's site.

Data reported on or entered in the CRF and are transcribed from source documents must be consistent with the source documents or the discrepancies must be explained. The investigator may need to request previous medical records or transfer records, depending on the study. Also, current medical records must be available.

Definition of what constitutes source data can be found in Section [10.1.7](#).

10.1.9. Study and Site Start and Closure**First act of recruitment**

The study start date is the date on which the clinical study will be open for recruitment of participants.

Study or site termination

The sponsor or sponsor's designee reserves the right to close the study site or terminate the study at any time for any reason at the sole discretion of the sponsor. Study sites will be closed upon study completion. A study site is considered closed when all required documents and study supplies have been collected and a study site closure visit has been performed.

The investigator may initiate study site closure at any time, provided there is reasonable cause and sufficient notice is given in advance of the intended termination.

Reasons for the early closure of a study site by the sponsor or investigator may include but are not limited to

- study termination
 - discontinuation of further study intervention development
- site termination

- failure of the investigator to comply with the protocol, the requirements of the IRB/IEC or local health authorities, the sponsor's procedures, or GCP guidelines
- inadequate recruitment (evaluated after a reasonable amount of time) of participants by the investigator, or
- total number of participants included earlier than expected.

If the study is prematurely terminated or suspended, the sponsor shall promptly inform the investigators, the IECs/IRBs, the regulatory authorities, and any contract research organization(s) used in the study of the reason for termination or suspension, as specified by the applicable regulatory requirements. The investigator shall promptly inform the participant and should assure appropriate participant therapy and/or follow-up.

10.1.10. Publication Policy

In accordance with the sponsor's publication policy, the results of this study will be submitted for publication by a peer-reviewed journal.

10.1.11. Investigator Information

Researchers with appropriate education, training, and experience, as determined by the sponsor, will participate as investigators in this clinical trial.

10.1.12. Sample Retention

Sample retention enables use of new technologies, response to regulatory questions, and investigation of variable response that may not be observed until later in the development of LY3561774 or after LY3561774 become(s) commercially available.

Sample Type	Custodian	Retention Period After Last Patient Visit^a
Exploratory Biomarkers	Sponsor or Designee	7 years
PK	Sponsor or Designee	1 year
Genetics	Sponsor or Designee	7 years
Immunogenicity	Sponsor or Designee	7 years

^aRetention periods may differ locally.

10.2. Appendix 2: Clinical Laboratory Tests

The tests detailed in the table below will be performed by the Lilly-designated laboratory or by the local laboratory as specified in the table below.

In circumstances where the sponsor approves local laboratory testing in lieu of Lilly-designated laboratory testing, the local laboratory must be qualified in accordance with applicable local regulations.

Protocol-specific requirements for inclusion or exclusion of participants are detailed in Section 5 of the protocol.

Additional tests may be performed at any time during the study as determined necessary by the investigator or required by local regulations.

Investigators must document their review of the laboratory safety results.

Laboratory results that could unblind the study will not be reported to investigative sites or other blinded personnel.

Clinical Laboratory Tests	Comments
Hematology	Assayed by Lilly-designated laboratory.
Hemoglobin	
Hematocrit	
Erythrocyte count (RBCs - red blood cells)	
Mean cell volume	
Mean cell hemoglobin	
Mean cell hemoglobin concentration	
Leukocytes (WBCs - white blood cells)	
Differential	
Percent and Absolute Count of:	
Neutrophils, segmented	
Bands	
Lymphocytes	
Monocytes	
Eosinophils	
Basophils	
Platelets	
Cell morphology (RBC and WBC)	
Clinical Chemistry	Assayed by Lilly-designated laboratory.
Sodium	
Potassium	
Chloride	
Bicarbonate	
Total bilirubin	
Direct bilirubin	
Alkaline phosphatase (ALP)	
Alanine aminotransferase (ALT)	
Aspartate aminotransferase (AST)	
Gamma-glutamyl transferase (GGT)	
Blood urea nitrogen (BUN)	
Creatinine	
Creatine kinase (CK)	
Uric acid	
Total protein	
Albumin	
Calcium	
Phosphorus	
Glucose	
Amylase	
Lipase	
LDH	
Lipid Panel	Assayed by Lilly-designated laboratory.

Clinical Laboratory Tests	Comments
	After randomization, results will not be provided to investigative sites.
High-density lipoprotein cholesterol (HDL-C)	
Non-HDL-C	
Low-density lipoprotein cholesterol (LDL-C) direct	
Very-low-density lipoprotein cholesterol (VLDL-C)	
Cholesterol	
Triglycerides	
Coagulation Panel	Assayed by Lilly-designated laboratory.
PT-INR	
aPTT	
Urinalysis	Assayed by Lilly-designated laboratory.
Specific gravity	
pH	
Protein	
Glucose	
Ketones	
Bilirubin	
Urobilinogen	
Blood	
Nitrite	
Urine leukocyte esterase	
Microscopic examination of sediment	
Hormones (female)	
Follicle-stimulating hormone (FSH)	Assayed by Lilly-designated laboratory.
Urine pregnancy	Local laboratory.
Serum pregnancy	Assayed by Lilly-designated laboratory.
Urine Chemistry	Assayed by Lilly-designated laboratory.
Albumin	
Creatinine	
Calculations	Generated by Lilly-designated laboratory.
eGFR (CKD-EPI)	
Urinary albumin/creatinine ratio (UACR)	
HIV and Hepatitis Serology	Assayed by Lilly-designated laboratory.
HIV testing	
Hepatitis C virus (HCV) testing:	
HCV antibody	
Hepatitis B virus (HBV) testing:	
Hepatitis B surface antigen (HBsAg)	
Pharmacokinetic Samples	Assayed by Lilly-designated laboratory. Results will not be provided to the investigative sites.

Clinical Laboratory Tests	Comments
LY3561774 concentration	
Additional Testing	Assayed by Lilly-designated laboratory.
HbA1c	
C-reactive protein, high-sensitivity (hsCRP)	Results will not be provided to investigative sites.
ANGPTL3 and ANGPTL3/8	Results will not be provided to investigative sites.
ApoB	After randomization, only Day 270 results will be provided to investigative site.
ApoA-I,	Results will not be provided to investigative sites.
ApoC-III	Results will not be provided to investigative sites.
TSH	
Insulin	
Genetics Sample	Assayed by Lilly-designated laboratory. Results will not be provided to the investigative sites.
Exploratory Biomarker Storage Samples	Assayed by Lilly-designated laboratory. Results will not be provided to the investigative sites.
Serum	
Plasma (EDTA)	
Immunogenicity Samples	Assayed by Lilly-designated laboratory. Results will not be provided to the investigative sites.
Anti-LY3561774 antibodies	

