4.1.1. Design Outline

Screening

Interested participants will sign the appropriate informed consent document(s) prior to completion of any procedures.

The investigator will review symptoms, risk factors, medical history, concomitant medications and other inclusion and exclusion criteria prior to any diagnostic procedures. If the participant is eligible after this review, then the site will perform the diagnostic procedures to confirm eligibility.

Double-blind treatment and assessment period

This is the general flow during the treatment and assessment period:

- Complete MRI at any date prior to randomization
- Complete baseline procedures and sample collection
- Participants are randomly assigned to an intervention group, and
- Participants complete all visit procedures including efficacy assessments, safety monitoring, study intervention dosing, and post-dosing sample collection.

Safety follow-up

If a participant's ApoB levels do not return to $\geq 80\%$ of baseline on Day 270, then they will continue to the follow-up visit at Day 360.

If a participant's ApoB levels return to $\geq 80\%$ of baseline on Day 270, then Day 270 is their last study visit.

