6.3. Measures to Minimize Bias: Randomization and Blinding

Randomization

All participants will be centrally assigned to randomized study intervention using an IWRS. Before the study is initiated, the log in information and directions for the IWRS will be provided to each site.

Participants will be randomly assigned in a 2:1:2:2 ratio to placebo: LY3561774 100 mg:400 mg:800 mg. Placebo participants will be randomly assigned so that each dose cohort will have a matching placebo cohort that receives the same dose volume to maintain the study blind.

Participants will be stratified according to the Visit 1 TG level of <250 mg/dL and \geq 250 mg/dL.

Maintaining blinding

Investigators will remain blinded to each participant's assigned study intervention within each dose group, throughout the course of the study. To maintain this blind, an otherwise unblinded third party will be responsible for the receiving, registering, preparing, and administering of all study intervention. Although the participant and the investigator will know the injection volume, they will not know whether the participant is receiving LY3561774 or placebo. To mitigate the risk of unblinding due to color difference between IMPs, site will be trained on additional operational procedures. Unblinded personnel who administer IMP to participants at Visit 2 will have no other interaction, role, or responsibilities other than receiving, registering, preparing, and administering IMP at Visit 6 in the trial. Participants should be instructed to look away during IMP administration.

Emergency unblinding

The IWRS will be programmed with blind-breaking instructions. In case of an emergency, the investigator has the sole responsibility for determining if unblinding of a participant's intervention assignment is warranted. Participant safety must always be the first consideration in making such a determination.

If a participant's intervention assignment is unblinded, the sponsor must be notified immediately within 24 hours of this occurrence. The date and reason that the blind was broken must be recorded.

Discontinuation from the study in case of unblinding

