9.3. Statistical Analyses

9.3.1. General Considerations

Statistical analysis of this study will be the responsibility of Lilly or its designee.

Any change to the data analysis methods described in the protocol will require an amendment ONLY if it changes a principal feature of the protocol. Any other change to the data analysis methods described in the protocol, and the justification for making the change, will be described in the CSR. Additional exploratory analyses of the data will be conducted as deemed appropriate.

Unless otherwise noted, all tests of treatment effects will be conducted at a 2-sided alpha level of 0.05, and confidence intervals will be calculated at 95%, 2-sided. All tests of interactions between treatment groups and other factors will be conducted at a 2-sided alpha level of 0.10.

Baseline is defined as the last non-missing measurement recorded on or before the randomization visit, prior to first dose of intervention, unless otherwise specified.

Primary estimand of interest and efficacy assessment

The primary estimand is a precise definition of the treatment effect to be estimated. The primary estimand of interest is comparing efficacy of LY3561774 doses to placebo and is named the “efficacy estimand” (Section 3). The efficacy estimand represents the efficacy prior to discontinuation of intervention.

The primary efficacy assessment guided by the efficacy estimand will be conducted using the EAS (Section 9.2).

Safety assessments

Unless specified otherwise, safety assessments will be guided by an estimand comparing safety of LY3561774 doses with placebo irrespective of adherence to intervention. Thus, safety analyses will be conducted using the SS (Section 9.2).

Exploratory analyses

Additional exploratory analyses of the data will be conducted as deemed appropriate.

Continuous data

Continuous data will be summarized by the sample size, mean, SD, median, minimum, and maximum.

Categorical data

Categorical data will be summarized by sample size, frequency, and percentage.

Analysis models for the comparison among treatment groups

The analysis model for comparisons among treatment groups relative to continuous measurements assessed over time, in addition to the baseline and end of treatment measurements, will be an MMRM. The model terms are

- treatment
- visit
- treatment-by-visit interaction
- baseline measurement, and
- Visit 1 TG stratum ($<250\text{mg/dL}$, $\geq 250\text{ mg/dL}$).

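### Releasing the Day 270 ApoB to sites, together with the 80% rule, lets investigators infer likely active treatment in participants who continue to Day 360, although the protocol says the blind holds to study completion

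*Protocol*

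**What the plan says.** Protocol 10.2 (Appendix 2) sets a general rule: "Laboratory results that could unblind the study will not be reported to investigative sites or other blinded personnel". It applies that rule to the lipid panel ("After randomization, results will not be provided to investigative sites") and also withholds ANGPTL3, ApoA-I and ApoC-III. The ApoB row differs: "After randomization, only Day 270 results will be provided to investigative site".

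Protocol 4.1.1 (also 1.1 and 1.3, and SAP 1.2) makes the same Day 270 value decide follow-up. Participants below 80% of baseline return at Day 360 (Visit 801). For those at or above 80%, the wording ends: "of baseline on Day 270, then Day 270 is their last study visit".

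On blinding, Protocol 6.3 says: "Although the participant and the investigator will know the injection volume, they will not know whether the participant is receiving LY3561774 or placebo". Protocol 9.4 says: "Participants and investigators will remain blinded until the completion of the study". For a participant who continues, the last visit is Day 360.

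The safety set in Protocol 9.2 and SAP 3 includes follow-up data. AEs are collected at Visit 801 (Protocol 1.3) and until participation ends (8.3.1).

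**The concern.** ApoB is the primary efficacy variable, and the plan withholds it, with the other lipid markers, at every other visit after randomization. That treats such values as able to unblind. The Day 270 release is an exception to that policy, and no section squares it with the blinding statements. Even without the number, being called for Day 360 tells the investigator that ApoB remains more than 20% below baseline, which should be uncommon on placebo.

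At stake are the investigator's judgements after the result arrives: which AEs are noticed, how severe they are, and whether they are attributed to study drug. Protocol 10.3.4 also lets causality be revised later. These judgements reach the analysis: SAP 4.6.2 summarizes AEs by maximum severity and by relationship to study drug, by arm. One trigger for unblinded committee review in Protocol 10.1.5 rests on the investigator's own severity and relatedness calls. Protocol 4.2 relies on the double blind to limit bias in the safety assessments.

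**Working it through.** **1. The plan's own figures.** Protocol 9.5: 175 participants in 2:1:2:2 gives 50/25/50/50; after 20% dropout, 40/20/40/40. With SD 15 and a difference of 30:

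- 40 v 40: SE = 15 × √(1/40 + 1/40) = 3.35; 30/3.35 = 8.94.
- 40 v 20: SE = 15 × √(1/40 + 1/20) = 4.11; 30/4.11 = 7.30.

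Both exceed 1.96 by more than 5, so power is above 99.99%, in line with the stated figure of more than 99%. The planning values can be used as inputs.

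**2. Inputs for the inference.**

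- Allocation (Protocol 6.3): active to placebo 5:2, so the prior is 5/7 = 71.4%.
- Threshold (Protocol 4.1.1): a fall of more than 20% from baseline.
- SD 15 percentage points (Protocol 9.5), a Day 180 planning value carried to Day 270 by assumption.
- Assumed: normal percent change, placebo mean 0, equal dropout across arms, and active effect e common to all doses. No Day 270 effect is given; the Phase 1 effect data in Protocol 2.2 stop at Day 169. I therefore use a range.

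**3. Probability of continuing.**

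- Placebo: p = Φ(-20/15) = Φ(-1.333) = 0.0912.
- Active: a = Φ((-20 - e)/15), which is 0.7475, 0.5000 and 0.2525 for e = -30, -20 and -10.

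**4. Probability of active treatment, by Bayes' rule.** Among those who continue it is 5a/(5a + 2p):

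- e = -30: 3.7375/(3.7375 + 0.1824) = 0.953
- e = -20: 2.5000/(2.5000 + 0.1824) = 0.932
- e = -10: 1.2625/(1.2625 + 0.1824) = 0.874

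Among those who stop at Day 270 it is 5(1 - a)/(5(1 - a) + 2(1 - p)). Expected numbers use 100 active and 40 placebo completers.

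| Active effect at Day 270 | Active continuing | Placebo continuing | P(active), continues | P(active), stops | Continuing, active v placebo |
|---|---|---|---|---|---|
| -30% | 74.8% | 9.1% | 95.3% | 41.0% | 74.8 v 3.6 |
| -20% | 50.0% | 9.1% | 93.2% | 57.9% | 50.0 v 3.6 |
| -10% | 25.2% | 9.1% | 87.4% | 67.3% | 25.2 v 3.6 |

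**5. Sensitivity of P(active), continues.**

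- Smaller effect: 81.3% at -5%; 71.4% (no information) at 0.
- SD 10 to 20%, effect -10 to -30%: 83% to 99%.
- Effect differing by dose (100/400/800 mg): -10/-20/-30% gives 93.8%; 0/-10/-20% gives 89.7%.
- Strong waning, 0/-5/-10%: the doses continue at 0.091, 0.159 and 0.252. Weighted 1:2:2, the sum is 0.091 + 0.318 + 0.504 = 0.913, and 0.913/(0.913 + 0.182) = 83%. Only 0.913/5 = 18% of active participants would then continue.

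**6. What the exact value adds.** For a released change v the probability is 5f/(5f + 2), with f = exp{[v² - (v - e)²]/450}, where 450 = 2 × 15². At v = -40: e = -30 gives f = exp(1500/450) = 28.0 and 98.6%; e = -15 gives f = exp(975/450) = 8.7 and 95.6%. Just at the threshold, v = -20, the figures are 83.0% and 85.2%. The value therefore discriminates among those who continue in a way that a yes/no flag does not.

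**The case against.** The release looks deliberate: it appears to serve the 80% rule, and the ApoB row can be read as a specific exception to the general rule in 10.2. That explains it, but neither 10.2 nor 9.4 states the exception, and the sentence in 9.4 is unqualified.

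A reader might infer that investigators are effectively unblinded for every participant over the last 90 days. The documents do not support that. Participants at or above 80% leave at Day 270, and stopping leaves them at 41% to 67% active in the scenarios above. For those who continue, the result is a shift in probability, not knowledge of assignment. It rests on Day 180 planning values carried to about 180 days after the second dose, and Protocol 4.3 expects low efficacy at 100 mg. This objection stands and sets the scope of the point.

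The consequences are also bounded. All primary and secondary lipid endpoints are sampled by Day 270, before any release. Listed cardiovascular events and deaths go to a blinded external committee (Protocol 8.3.5 and 10.1.5; SAP 4.6.7.4). This stands too.

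A reader might also infer that sites would apply the 80% rule to the Visit 1 value for want of the Visit 2 result. That rests on silence. The documents do not say who applies the rule, whether the restriction runs from sample date or report date, or whether the laboratory reports a ratio.

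Finally, a flag in place of the value leaves the yes/no inference in step 4 unchanged. That is correct, and it is why the flag alone is not a sufficient fix.

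**Conclusion.** The conflict is in the text. Protocol 10.2 releases a result that its own general rule would withhold, and 9.4 claims a blind to study completion that the design does not deliver for participants who continue to Day 360. For them, the probability of active treatment rises from 71% to about 95%, 93% or 87% for a Day 270 effect of -30%, -20% or -10%. This assumes SD 15%, no placebo change and a common effect. It falls to about 83% in the waned, dose-dependent case, and to no shift if the effect is gone.

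The exposure is confined to investigator-reported AE detection, severity and causality after the result is released. The efficacy endpoints and the external adjudication keep their blind. This is a limited weakness in the late safety data together with an inaccurate blinding statement; the trial's blind as a whole is not broken.

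**What to change.** Reconcile Protocol 4.1.1, 9.4 and the two statements in 10.2, leaving the 80% rule as it is:

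1. Amend the ApoB row in 10.2 so that no post-randomization ApoB value goes to sites.
2. Have the central laboratory or IWRS compare Day 270 ApoB with the baseline defined in Protocol 9.3.1 ("Baseline is defined as the last non-missing measurement recorded on or before the randomization visit", and before first dose) and send the site only whether Visit 801 is required.
3. Send that flag only after the investigator has signed AE severity and causality through Visit 12.
4. Because the flag is itself informative, restate 9.4: for participants who continue, the site-level blind is protected only to Day 270.
5. In the SAP, tabulate AEs after Day 270 separately, noting that allocation could be inferred.

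Steps 1 and 2 remove the extra information in the exact value; step 3 protects judgements on events up to Day 270; steps 4 and 5 describe what cannot be removed. The cost is a small laboratory/IWRS set-up change, edits to the protocol wording, one more safety table, a wait for the flag at the site, and a less favourable blinding statement. No extra participants or procedures are needed.
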